9.4 Safety Analysis

All safety analyses will be performed based on the Safety Set by cohort and overall.

The overall safety profile of VX-147 will be assessed in terms of the following safety and tolerability endpoints:

- Incidence of treatment-emergent adverse events (TEAEs)
- Clinical laboratory values (hematology, serum chemistry, coagulation studies, and urinalysis)
- Standard 12-lead ECG outcomes
- Vital signs

Only descriptive analyses of safety will be performed, and no statistical hypothesis testing will be performed.

9.4.1 Adverse Events

AEs will be coded according to MedDRA. For analysis purposes, AEs will be classified as pretreatment AEs and TEAEs as follows:

Pretreatment AEs: AEs that occurred before the first dose of study drug

Treatment-emergent AEs: AEs that worsened or started on or after the first dose date of study drug through the end of the TE Period

For AEs with completely missing or partial start dates, if there is no clear evidence that the AEs started before or after the first dose of study drug, the AEs will be classified as TEAEs.

Imputation rules for missing or partial AE start date are defined as [Appendix C](#).

AE summary tables will be presented only for TEAEs, and will include the following:

- All TEAEs
- TEAEs by strongest relationship
- TEAEs by maximum severity
- TEAEs leading to treatment discontinuation
- TEAEs leading to treatment interruption
- Related TEAEs
- Serious TEAEs

- Related serious TEAEs
- TEAEs leading to death

Summaries will be presented by MedDRA SOC and PT using frequency counts and percentages (i.e., number and percentage of subjects with an event). When summarizing the number and percentage of subjects with an event, subjects with multiple occurrences of the same AE or a continuing AE will be counted once, and only the maximum severity level will be presented in the severity summaries, and the strongest relationship level in the relationship summaries.

All AEs, including pretreatment AEs and TEAEs will be presented in an individual subject data listing based on the All Subjects Set. In addition, a listing containing individual subject adverse event data for TEAEs leading to treatment discontinuation, TEAEs leading to treatment interruption, SAEs and all deaths will be provided separately.

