p-nCG (urine)	X				X	X	X	X	(Sections 11.6.2 and 11.6.5). This can be collected in the same sample as the urine sample for efficacy, safety, and biomarker analysis.
VX-147 dosing				X		The last dose of Treatment Period 1 will be Day 14. The first dose of Treatment Period 2 will be on Day 15 after all predose assessments are completed. The last day of dosing will occur the day before the Week 13 visit. The first dose in each period must be administered under the supervision of site medical staff or a home health nurse. Subjects will be monitored for 4 hours after receiving the first dose of each Treatment Period. (Section 9.6).			

^c Day 1 urinalysis will be for safety and biomarker assessments. Efficacy assessments will not be done.

Protocol VX19-147-101, Version 6.0

Table 3-2 Study VX19-147-101: Part A Treatment Period 1, Treatment Period 2, and Early Termination of Treatment Visit

	Treatmen	nt Period 1		Trea	atment Perio	od 2			
	Day 1 Visit	Week 1 Visit	Day 15 Visit	Week 3 Visit	Week 5 Visit	Week 9 Visit	Week 13 Visit	Early	
Event/ Assessment ^a	Window: Day 1 (±0 days)	Window: Day 8 (±1 day)	Window: Day 15 (±2 days)	Window: Day 22 (±2 days)	Window: Day 36 (±2 days)	Window: Day 64 (±2 days)	Window: Day 92 (-2 days)	Termination of Treatment Visit ^b	Comments
Adverse events			Continu	ous from signi	ng of ICF th	rough SFUV			Section 11.6.1.
Medications review			Continu	ous from signi	ing of ICF th	rough SFUV			Section 9.4.

Table 3-3 Study VX19-147-101: Postdose PK Sampling, Safety Follow-up Visit, and Part B Off-treatment Follow-up Period

Event/Assessment	Postdose PK Sampling	SFUV 28 (± 7) Days	Part B: Optional Off-treatment Follow-up	Comments
	(Approximately 48 hours after the last dose of study drug) ^a	After Last Dose of Study Drug ^b	Visits ^c (Part B Week 4 ^b , 8, and 12)	
Subject visit	X	X	X (until UPCR returns to ≥90% of baseline level)	The visit may be performed by a home health visit or in the clinic at the discretion of the investigator (Section 9.3.5). For each visit, at least 1 interaction with the subject and investigator will occur by phone, video, or in the clinic (i.e., in person, phone, or telemedicine video conference) within 1 business day after the home health visit, which can be outside the visit window. See Section 9.1.3 for details about determining the last visit for Part B.
SF-36		X		To be completed before all other study assessments (Section 11.5.3).

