9.3.3 Study Drug Dose

The administration of once daily doses of 15 mg and 45 mg were selected on the totality of clinical safety, tolerability, and PK from the FIH study (Study 001); as well as toxicology and non-clinical pharmacodynamic (PD) data.

In Study 001, single ascending oral doses of VX-147 up to 50 mg and multiple ascending doses of VX-147 up to 45 mg once daily for 14 days were evaluated. The doses were well-tolerated and no clinically significant safety concerns were identified. In this study, a low dose of 15 mg once daily is selected to characterize the PK in FSGS patients and to assess any measurable decrease in proteinuria. Based on an exposure-response model, the exposures from the 15 mg dose are expected to result in approximately 90% inhibition in the in vitro ion flux model. This level of inhibition may result in a measurable decrease in proteinuria after 2 weeks of dosing.

A high dose of 45 mg once daily is selected to maximize the probability of reduction in proteinuria over the 11-week dosing period. Based on the exposure-response model referenced above, exposures from this dose are expected to result in over 96% inhibition in the in vitro ion flux model. VX-147 exposure from the 2 doses are expected to be well differentiated based on data from the FIH healthy subject study (Study 001). Thus, the doses selected will provide an adequate assessment of the dose-response relationship and safety profile of VX-147 in the exposure range of interest.

Additional information about FIH and nonclinical data are available in the Investigator's Brochure.

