7 STUDY DESIGN

7.1 Overall Design

This is a single-arm, open-label, 2-part study. In Part A, all subjects will receive VX-147 at a dosage of 15 mg qd for 2 weeks and VX-147 at a dosage of 45 mg qd for 11 weeks. Part A will be enrolled in 2 cohorts: Cohort 1 and an optional Cohort 2. Cohort 1 includes approximately 10 subjects with UPCR approximately ≥ 3 g/g and < 10 g/g and eGFR approximately ≥ 30 mL/min/1.73 m². Optional Cohort 2 includes approximately 10 subjects with UPCR approximately ≥ 0.8 g/g and < 2.7 g/g and eGFR approximately ≥ 30 mL/min/1.73 m².

[figure not shown]
Subjects in Cohort 1 and Cohort 2 are permitted to take a stable low dose of systemic corticosteroid (prednisone ≤ 10 mg per day or prednisone equivalent) and/or an allowed immunosuppressant (i.e., tacrolimus, mycophenolate, or cyclosporine).

Enrollment of Cohort 1 and Cohort 2 will be managed through the interactive web response system (IWRS).

In Optional Part B, subjects will be followed for up to 12 weeks for evaluation of proteinuria off-treatment (Section 9.1.3 of the CSP).

All subjects will complete a SFUV at 28 (± 7) days after the last dose of study drug.

Figure 7-1 VX19-147-101 Study Design

D: Day; PK: pharmacokinetics; qd: once daily; UPCR: urine protein to creatinine ratio; W: Week

Notes: The figure is not drawn to scale. After completing Part A, subjects will be followed monthly for up to 12 weeks or until UPCR returns to baseline, whichever occurs first. All subjects will be required to complete a SFUV at 28 (± 7) days after the last dose of study drug.

^a Proteinuria will be assessed at multiple timepoints throughout the Treatment Period and Off-treatment Follow-up. Triangles represent timepoints for the primary analysis.

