9 STATISTICAL ANALYSIS

9.1 General Considerations

The Schedule of Assessments is provided in Section 3 of the CSP. The precision standards for reporting variables are provided in an internal Biometrics document that specifies the programming rules including the precision for derived variables.

Continuous variables will be summarized using the following descriptive summary statistics: the number of subjects (n), mean, SD, median, minimum value (min), and maximum value (max).

Categorical variables will be summarized using counts and percentages.

Baseline value, unless specified otherwise, will be defined as the most recent non-missing measurement (scheduled or unscheduled) collected before the first dose of study drug in the Treatment Period. For ECGs, baseline will be defined as the most recent pretreatment measurement (or the average of triplicate measurements, if the most recent pretreatment measurement is obtained in triplicate) before the first dose of study drug in the Treatment Period. For systolic and diastolic blood pressure, baseline will be defined as the most recent pretreatment measurement (or the average of triplicate measurements, if the most recent pretreatment measurement is obtained in triplicate) before the first dose of study drug in the Treatment Period. For UPCR (and UACR) data baseline value will be the average of UPCR (UACR) values from the 3 urine samples collected during screening for the purpose of assessing eligibility.

Change (absolute change) from baseline will be calculated as Post-baseline value – Baseline value.

Treatment-emergent (TE) Period will include the time from the first dose of study drug in the Treatment Period to either (1) the Safety Follow-up Visit, (2) ETT Visit if it replaces the Safety Follow-up Visit, or (3) the date of the last dose + 28 days for subjects who do not have a Safety Follow-up Visit. The TE Period will be used for safety analyses unless specified otherwise.

Unscheduled visits: Data obtained from unscheduled visits will be included in the analysis as follows:

- In scheduled visit windows per specified visit windowing rules
- In the derivation of baseline
- In the derivation of maximum and minimum values during TE period, and maximum and minimum change from baseline values during TE period for safety analyses
- In individual subject data listings as appropriate

Visit Window: The analysis visit windows for the protocol-defined visits are provided in [Appendix A](#).

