9.2.5 Study Drug Exposure and Compliance

Study drug exposure (in days) will be calculated as (last date of dosing – first date of dosing) + 1, regardless of study drug interruption, and will be summarized descriptively based on the Safety Set by cohort and overall. Study drug exposure (in weeks) will be summarized in categories for Treatment Period: ≤ 1 week, >1 to ≤ 2 weeks, >2 to ≤ 3 weeks, >3 to ≤ 5 weeks, >5 to ≤ 9 weeks, >9 to ≤ 12 weeks, and >12 weeks using counts and percentages.

Study drug compliance will be calculated as $100 \times [1 - (\text{total number of days of study drug interruption}) / (\text{duration of study drug exposure in days})]$. A study drug interruption on a given day is defined as any interruption of the study drug on that day. A study drug interruption that continues through the end of the study participation (i.e., subject does not resume study drug before the end of the study participation) will not be included in the compliance calculation. Study drug compliance will be summarized descriptively based on the FAS by cohort and overall. It will also be summarized in categories: $<80\%$ and $\geq 80\%$, using counts and percentages.

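### The TEAE tables in SAP 9.4.1 do not show whether events began on 15 mg, on 45 mg or after the last dose

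*SAP*

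**What the plan says.** SAP 7.1 gives all subjects "VX-147 at a dosage of 15 mg qd for 2 weeks and VX-147 at a dosage of 45 mg qd for 11 weeks". The schedule in Protocol version 6.0, Table 3-2, fixes the boundaries: "The last dose of Treatment Period 1 will be Day 14" and "The last day of dosing will occur the day before the Week 13 visit".

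SAP 9.1 sets the window for safety: "Treatment-emergent (TE) Period will include the time from the first dose of study drug in the Treatment Period to either (1) the Safety Follow-up Visit", or to an Early Termination of Treatment Visit that replaces that visit, or to 28 days after the last dose. SAP 9.4.1 applies it to adverse events: "Treatment-emergent AEs: AEs that worsened or started on or after the first dose date of study drug through the end of the TE Period". A subject with repeat or continuing occurrences of the same event is counted once across the window.

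On table columns, SAP 9.4 says: "All safety analyses will be performed based on the Safety Set by cohort and overall". The laboratory, ECG and vital-sign threshold counts and the maximum QT/QTcF categories (SAP 9.4.2 to 9.4.4) use the same window. Protocol 12.3.4 adds no split by treatment period.

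On the choice of doses, Protocol 9.3.3 concludes: "Thus, the doses selected will provide an adequate assessment of the dose-response relationship and safety profile of VX-147 in the exposure range of interest".

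**The concern.** The cohorts differ in baseline proteinuria, not in treatment, so the by-cohort columns say nothing about dose. Each column (Cohort 1, Cohort 2, overall) combines time on 15 mg, time on 45 mg and time after dosing. A TEAE row gives the number of subjects affected, without showing when the events began relative to the dose step or the last dose.

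Safety and tolerability is a secondary objective, and Protocol 9.3.1 describes this as the first study in patients with FSGS. Timing of onset against a threefold dose increase is among the first things a reader of such a study asks about. The plan does show timing elsewhere: UPCR is reported at Week 1, Day 15 and each later visit, and laboratory, ECG and vital-sign values are summarized by visit. The AE tables and the threshold counts are the exception.

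**Working it through.** **Inputs**
- 15 mg: Day 1 to Day 14, so 14 days (Protocol Table 3-2).
- 45 mg: from Day 15 to the day before the Week 13 visit. With that visit on its target, Day 92, the last dose is on Day 91, so 91 − 14 = 77 days.
- After the last dose: 28 (± 7) days to the SFUV, so 21 to 35 days (SAP 7.1).

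**Check against the plan's own durations.** 14 days = 2 weeks, 77 days = 11 weeks and 91 days = 13 weeks, which agrees with SAP 7.1 and Protocol 9.3.1.

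**Share of the TE window by dose state, for a completer**

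| SFUV after last dose | Window (days) | 15 mg | 45 mg | After last dose | Not on 45 mg |
|---|---|---|---|---|---|
| 21 days | 91 + 21 = 112 | 14/112 = 12.5% | 77/112 = 68.8% | 21/112 = 18.8% | 35/112 = 31.3% |
| 28 days | 91 + 28 = 119 | 14/119 = 11.8% | 77/119 = 64.7% | 28/119 = 23.5% | 42/119 = 35.3% |
| 35 days | 91 + 35 = 126 | 14/126 = 11.1% | 77/126 = 61.1% | 35/126 = 27.8% | 49/126 = 38.9% |

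The Week 13 visit may be up to 2 days early. At Day 90, with the SFUV at 28 days, the share not on 45 mg is 42/117 = 35.9%, which is little different.

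**Why the pooled row cannot show timing.** Take constant daily hazards; the rates are assumed for illustration and are not in the documents. Cumulative hazard is rate × days, and incidence is 1 − exp(−cumulative hazard).
- Pattern A: 0.004 per day on 45 mg and zero otherwise. The cumulative hazard is 0.004 × 77 = 0.308, and the pooled incidence is 26.5%, all of it on 45 mg.
- Pattern B: the same 0.308 spread evenly over 119 days, or 0.308/119 = 0.00259 per day. The pooled incidence is again 26.5%, but the period incidences are 3.6% (14 days), 18.1% (77 days) and 7.0% (28 days).

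The planned table would have the same expected row for both. A table by onset period would have different ones.

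**Data available.** Protocol 13.1.1.3 records the date of first occurrence of every AE, and the first dose of each treatment period is supervised. The split needs no new data.

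**The case against.** The case against has several sound parts.

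- **No protocol–SAP conflict.** A reader might infer from Protocol 9.3.3 that safety by dose was promised. The sentence speaks of the dose-response relationship and the safety profile and does not say that AE incidence will be tabulated by dose. Protocol 9.3.1 gives PK at two dose levels as the reason for using two doses. The SAP follows Protocol 12.3.4. This stands.
- **The information is not lost.** SAP 9.4.1 lists every AE by subject. SAP 9.4.2 to 9.4.4 list out-of-range laboratory values and all ECG and vital-sign values. ECGs are summarized at Day 15 predose and 2 hours postdose. With about 20 subjects, a reader could place events by period. This stands, and it limits the point to the AE and threshold tables. Even so, listings leave each reader to build the summary.
- **Concentration-response for AEs is planned** (Protocol 12.4.2). That analysis is exploratory and belongs to a separate plan, so it does not replace an incidence table.
- **Exposure is already informative.** SAP 9.2.5 states: "Study drug exposure (in weeks) will be summarized in categories for Treatment Period". One cut-point is at 2 weeks. Since dose modifications are not allowed, exposure beyond 2 weeks nominally identifies those who reached 45 mg. Separate exposure by dose would add little.
- **A split cannot isolate a dose effect.** All subjects follow one order without washout, for 14 and then 77 days. Late events may be delayed or cumulative, and events soon after stopping may still be drug-related. This stands.
- **Counts will be small.** At a true incidence of 10%, the chance of seeing at least one affected subject is 65% with 10 subjects and 88% with 20. Splitting every table by cohort and period would spread very few events over many columns.

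A reader might also infer that a fixed fraction of the reported events is wrongly credited to 45 mg. The documents do not support that. They give no event rate, the tables count subjects rather than events, and the SAP does not label the incidence as that of 45 mg alone.

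**Conclusion.** The planned TEAE tables do not show when events began relative to the step to 45 mg or the last dose. About 35% of the nominal window (31% to 39% across the SFUV window) is not on 45 mg. These shares assume a completer without interruptions whose Week 13 visit is on Day 92. They describe time at risk, not the fraction of events affected.

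The consequence is modest. Safety analysis is descriptive throughout, no estimate is wrong, and listings and by-visit summaries hold much of the information. One descriptive summary by onset period is still worth adding: it serves a secondary objective and uses dates already collected. It would show timing of onset and would not establish a dose effect.

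**What to change.** In SAP 9.4.1, add one summary for the overall Safety Set covering all, related and serious TEAEs by SOC and PT, with four columns by period of onset:
1. first 15 mg dose to before the first 45 mg dose;
2. first 45 mg dose to the last dose;
3. after the last dose;
4. total.

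Show the subjects entering each period and the subject-days in it. Assign events by date, with onset on the date of the first 45 mg dose placed in period 2, and state how a pre-existing event that worsens is dated. Note that a subject may count once in more than one period, so the columns need not add up to the total.

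Flag AEs with imputed onset. Appendix C can set a partial or missing start date to the first dose date, which would place the event in the 15 mg column by rule. State that period differences are descriptive because dose order is fixed and dose is confounded with time.

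Optionally, apply the same split to the maximum QTcF categories and the other threshold counts. Splitting further by cohort, or changing SAP 9.2.5, is not needed.

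Cost: a paragraph of SAP text and one extra table from existing data. The downside is small counts in each column.

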9.4.2 Clinical Laboratory

All statistical analyses of laboratory values will be performed using SI units. For treatment-emergent laboratory measurements, the observed values and change from baseline values of the continuous hematology, chemistry, and coagulation results will be summarized at each visit.

The number and percentage of subjects with selected test values meeting at least 1 threshold analysis criterion event during the TE period will be summarized. The threshold analysis criterion shift from baseline will also be summarized for selected laboratory test values. The threshold analysis criteria are provided in [Appendix D](#).

Results of urinalysis and the urine/serum pregnancy test will be in individual subject data listings only.

In addition, a listing of individual subject hematology, chemistry, and coagulation values outside the normal reference ranges will be provided. This listing will include data from both scheduled and unscheduled visits.

9.4.3 Electrocardiogram

For the treatment-emergent ECG measurements, a summary of observed values and change from baseline values will be provided at each visit and time point, as applicable, for the following ECG measurements: heart rate (HR; beats per minute [bpm]), PR (msec), RR (msec), QRS duration (msec), QT (msec), and QT corrected for HR intervals (QTcF [msec]). In addition, the number and percentage of subjects by maximum treatment-emergent value of QT/QTcF intervals, categorized as ≤ 450 msec, >450 msec and ≤ 480 msec, >480 msec and ≤ 500 msec, and >500 msec, as well as maximum treatment-emergent change from baseline value of QT/QTcF

intervals, categorized ≤ 0 msec, >0 to ≤ 30 msec, >30 and ≤ 60 msec, and >60 msec will be provided.

The number and percentage of subjects meeting at least 1 threshold analysis criterion during the TE period will be summarized. The threshold analysis criteria are provided in [Appendix D](#).

In addition, a listing containing individual subject ECG values will be provided. This listing will include data from both scheduled and unscheduled visits.

9.4.4 Vital Signs

For the treatment-emergent vital signs measurements, the observed values and change from baseline values will be summarized at each visit. The following vital signs parameters will be summarized: systolic and diastolic blood pressure (mm Hg), pulse rate (beats per minute), body temperature ($^{\circ}\text{C}$), and respiratory rate (breaths per minute).

The number and percentage of subjects meeting a threshold analysis criterion during the TE Period will be summarized. The threshold analysis criteria are provided in [Appendix D](#).

In addition, a listing containing individual subject vital signs values will be provided. This listing will include data from both scheduled and unscheduled visits.

9.4.5 Physical Examination

Physical examination (PE) results will be presented in individual subject data listings only.

9.4.6 Other Safety Analysis

Change from baseline in weight (kg) will be summarized at each visit.

9.4.7 COVID-19 Impacted Visits

A listing containing subjects' visits impacted due to COVID-19 will be provided.

9.5 Other Analyses

9.5.1 Analysis of SF-36

SF-36 is a patient-reported generic measure of health status. The questionnaire provides information about functional health and wellbeing, as well as 2 psychometrically based physical and mental health summary measures. Physical and mental component summary scores will be provided by commercially available software, i.e., QualityMetric Health OutcomesTM Scoring Software. Analysis of SF-36 will be conducted separately for Cohort 1 and Cohort 2, as well as combined.

Change from baseline in patient-reported outcome (PRO) Short Form Health Survey 36 (SF-36) over time during the Treatment Period: The change from baseline in the SF-36 physical component summary scores and the change from baseline in the SF-36 mental component summary scores will be summarized descriptively at Week 5 and Week 13.

Change from baseline in SF-36 at 4 weeks after the last dose (SFUV): The change from baseline in the SF-36 physical component summary scores and the change from baseline in the SF-36 mental component summary scores will be summarized descriptively at 4 weeks after the last dose of VX-147.

